### 8.2.2 Serious Adverse Events

A **serious adverse event** (SAE) is any adverse experience occurring at any dose that results in any of the following outcomes:

- Results in **death**.
- Is a **life-threatening** adverse experience. The term life-threatening in the definition of serious refers to an adverse event in which the subject was at risk of death at the time of the event. It does not refer to an adverse event which hypothetically might have caused death if it were more severe.

- Requires **inpatient hospitalization or prolongation of existing hospitalization**. Any adverse event leading to hospitalization or prolongation of hospitalization will be considered as Serious, UNLESS at least one of the following expectations is met:
  - The admission results in a hospital stay of less than 24 hours OR
  - The admission is pre-planned (e.g., elective or scheduled surgery arranged prior to the start of the study) OR
  - The admission is not associated with an adverse event (e.g., social hospitalization for purposes of respite care).

However it should be noted that invasive treatment during any hospitalization may fulfill the criteria of “medically important” and as such may be reportable as a serious adverse event dependent on clinical judgment. In addition where local regulatory authorities specifically require a more stringent definition, the local regulation takes precedent.

- Results in **persistent or significant disability/incapacity**. The definition of disability is a substantial disruption of a person’s ability to conduct normal life’s functions.
- Is a **congenital anomaly/birth defect**.
- Is an **important medical event**. Important medical events that may not result death, be life-threatening, or require hospitalization may be considered a serious adverse experience when, based upon appropriate medical judgment, they may jeopardize the subject and may require medical or surgical intervention to prevent one of the outcomes listed in this definition. Examples of such medical events include allergic bronchospasm requiring intensive treatment in an emergency room or at home, blood disease or disorders, or convulsions that do not result in inpatient hospitalization, or the development of drug dependency or drug abuse. The development of a new cancer is always considered an important medical event.

### **8.2.3 Adverse Event Evaluation**

The investigator or designee is responsible for ensuring that all adverse events (both serious and non-serious) observed by the clinical team or reported by the subject, which occur after the

subject has signed the informed consent are fully recorded in the subject's medical records. Source documentation must be available to support all adverse events.

The investigator or sub-investigator (treating physician if applicable) or delegated staff will provide the following for all adverse events (both serious and non-serious):

- Event term (as per CTCAE 4.1)
- Description of the event
- Date of onset and resolution
- **Expectedness of the toxicity**
- **Grade of toxicity**
- **Attribution of relatedness to the investigational agent- (this must be assigned by an investigator, sub-investigator, or treating physician)**
- Action taken as a result of the event, including but not limited to; no changes, dose interrupted, reduced, discontinued, etc. or action taken with regard to the event, i.e. no action, received conmed or other intervention, etc.
- Outcome of event

**An expected adverse event** is an event previously known or anticipated to result from participation in the research study or any underlying disease, disorder, or condition of the subject. The event is usually listed in the Investigator Brochure, consent form or research protocol.

**An unexpected adverse event** is an adverse event not previously known or anticipated to result from the research study or any underlying disease, disorder, or condition of the subject.

**Attribution** is the relationship between an adverse event or serious adverse event and the study drug. Attribution of any adverse event can only be assessed by the PI and/or Co-I. Attribution will be assigned as follows:

- Definite – The AE is clearly related to the study drug.
- Probable – The AE is likely related to the study drug.
- Possible – The AE may be related to the study drug.
- Unlikely – The AE is doubtfully related to the study drug.
- Unrelated – The AE is clearly NOT related to the study drug.

Protocol must specify if attribution is required for individual components of the treatment regimen or the treatment regimen as a whole.

### **8.3 SAE Report Form**

SAEs will be recorded on the FDA Form 3500A (MedWatch) and Study SAE coversheet but should only be reported as instructed below. The electronic FDA SAE reporting forms should not be used.

### **8.4 Reporting Procedures for Serious Adverse Events**

For the purposes of safety reporting, all adverse events will be reported that occur during treatment and through 30 days after the final dose of study drug. Adverse events, both serious and non-serious, and deaths that occur during this period will be recorded in the source documents. All SAEs should be monitored until they are resolved or are clearly determined to be due to a subject's stable or chronic condition or intercurrent illness(es). Related AEs will be followed until resolution to baseline or grade 1 or stabilization.

#### **8.4.1 SAE Reporting Requirements**

- Participating investigators (all sites) must report all serious adverse events to the Lead Site Principal Investigator (e.g. Sponsor-Investigator) within **24 hours** of discovery or notification of the event. The participating investigator must also provide follow-up information on the SAE until final resolution.
- The Lead Site Principal Investigator will review the SAE and report the event to the FDA, external collaborator(s), and IRB as applicable.
- It is the Sponsor-Investigator's responsibility (e.g. lead site PI) to ensure that ALL serious adverse events that occur on the study (e.g. ALL SAEs that occur at each enrolling institution) are reported to all participating sites.

#### **Institutional Review Board Reporting Requirements:**

- Investigative sites will report adverse events to their respective IRB according to the local IRB's policies and procedures in reporting adverse events.

## **8.5 SAEs and OnCore**

- All SAEs will be entered into OnCore.
- A copy of the SAE form(s) submitted to the sponsor-investigator is also uploaded into OnCore.

## **8.6 Data Safety and Toxicity Committee**

It is the responsibility of each site PI to ensure that ALL SAEs occurring on this trial (internal or external) are reported to the Case Comprehensive Cancer Center's Data and Safety Toxicity Committee. This submission is simultaneous with their submission to the sponsor and/or other regulatory bodies.

## **8.7 Data and Safety Monitoring Plan (DSMP)**

This protocol will adhere to the policies of the Case Comprehensive Cancer Center Data and Safety Monitoring Plan in accordance with NCI guidelines.

## **9.0 PHARMACEUTICAL INFORMATION**

A list of the adverse events and potential risks associated with the investigational or commercial agents administered in this study can be found in Section 8.1.

### **9.1 Investigational Agents**

**9.1.1 Name of Agent**      Azacitidine

Other Names:      Vidaza

**Product description:** Azacitidine is FDA approved and commercially available.

**Preparation for Intravenous Administration:** Reconstitute the appropriate number of azacitidine vials to achieve the desired dose. Reconstitute each vial with 10 mL sterile water for injection. Vigorously shake or roll the vial until all solids are dissolved. The resulting solution will contain azacitidine 10mg/mL. The solution should be clear. Parenteral drug product should be inspected visually for particulate matter and discoloration prior to administration, whenever solution and container permit.

Withdraw the required amount of azacitidine solution to deliver the desired dose and inject into a 50-100 mL infusion bag of either 0.9% Sodium Chloride Infusion or Lactated Ringer's Infusion.

Azacitidine is incompatible with 5% Dextrose solutions, Hespan, or solutions that contain bicarbonate. These solutions have the potential to increase the rate of degradation of azacitidine and should therefore be avoided.

**Intravenous Administration:** Azacitidine solution is administered intravenously. Administer the total dose over a period of 10-40 minutes. The administration must be completed within 1 hour of reconstitution of the azacitidine vial.

**Solution Stability:** Azacitidine reconstituted for intravenous administration may be stored at 25°C (77°F), but administration must be completed within 1 hour of reconstitution. If reconstituted azacitidine comes into contact with the skin, immediately and thoroughly wash with soap and water. If it comes into contact with mucous membranes, flush thoroughly with water. Reconstituted azacitidine may be stored for up to 1 hour at 25°C (77°F) or for up to 8 hours between 2 and 8°C (36 and 46°F). The azacitidine suspension is single-use and does not contain any preservatives. Unused portions of each vial should be discarded properly. Do not save any unused portions for later administration. It is recommended that 5-azacitidine in solution is administered as soon as possible.

**Storage:** Store reconstituted vials at 25o C (77o F); excursions permitted to 15o-30o C (59o-86o F) (See USP Controlled Room Temperature). There is no need to protect azacitidine from

exposure to light.

**Preparation for Subcutaneous Administration:** Reconstitute VIDAZA aseptically with 4 mL sterile water for injection. Inject the diluent slowly into the vial. Vigorously shake or roll the vial until a uniform suspension is achieved. The suspension will be cloudy. The resulting suspension will contain azacitidine 25 mg/mL. Do not filter the suspension after reconstitution. Doing so could remove the active substance.

**Preparation for Immediate Subcutaneous Administration:** Doses greater than 4 mL should be divided equally into 2 syringes. The product may be held at room temperature for up to 1 hour, but must be administered within 1 hour after reconstitution.

**Preparation for Delayed Subcutaneous Administration:** The reconstituted product may be kept in the vial or drawn into a syringe. Doses greater than 4 mL should be divided equally into 2 syringes. The product must be refrigerated immediately. When VIDAZA is reconstituted using water for injection that has not been refrigerated, the reconstituted product may be held under refrigerated conditions (2°C - 8°C, 36°F - 46°F) for up to 8 hours. When VIDAZA is reconstituted using refrigerated (2°C - 8°C, 36°F - 46°F) water for injection, the reconstituted product may be stored under refrigerated conditions (2°C - 8°C, 36°F - 46°F) for up to 22 hours. After removal from refrigerated conditions, the suspension may be allowed to equilibrate to room temperature for up to 30 minutes prior to administration.

**9.1.2 Name of Agent**      Ascorbic Acid

Other Names:      Vitamin C, 1000 mg

**Product description:** Ascorbic Acid is a tablet of 1000 mg Patient is to take one tablet once a day.

### **Product Description**

USP-Verified Dietary Supplement. Recommended by pharmacists. Antioxidant - Helps boost the immune system. Vitamin C helps neutralize free radicals and helps iron get absorbed in the body. UPS has tested and verified ingredients, potency and manufacturing process. USP sets official

standards for dietary supplements. No artificial colors. No artificial flavors. No preservatives. No chemical solvents, yeast or gluten. (These statements have not been evaluated by the Food and Drug Administration. This product is not intended to diagnose, treat, cure or prevent any disease).

**Brand:** Nature Made

This Nature Made product provides vitamin C, a versatile and essential vitamin critical for the proper functioning of our immune system. In addition, vitamin C helps manufacture certain nerve-transmitting substances and hormones while helping absorb and utilize other nutrients, such as vitamin E and iron. Vitamin C also makes collagen, which holds connective tissues together in skin, bone, teeth, and other parts of the body.

Vitamin C is an important and powerful antioxidant that works in the aqueous (water) environments of the body, such as the lungs and lens of the eye. Its primary antioxidant partners are vitamin E and the carotenes (such as beta-carotene), but it also works with the antioxidant enzymes. Vitamin C regenerates oxidized vitamin E and restores the antioxidant potential of vitamin E in the body.

Vitamin C is recommended as part of a daily regimen for women's and men's health, longevity, heart strength, and immunity.

- No artificial colors
- No artificial flavors
- No preservatives
- No chemical solvents, yeast or gluten. Recommended By Pharmacists.
- USP Standards plus Nature Made's Pure Ingredients guarantee optimum quality.  
Guaranteed purity, potency and dissolution.

**Safety Warning**

Do not use if imprinted seal under cap is broken or missing.

## Ingredients

Cellulose Gel, Hypromellose, Croscarmellose Sodium, Stearic Acid, Magnesium Stearate, Silicon Dioxide, Polyethylene Glycol, Vitamin C

## Directions

Suggested Use: Take one tablet daily with a meal. Keep bottle tightly closed. Store in a cool, dry place, out of reach of children.

## **10.0 EXPLORATORY or CORRELATIVE STUDIES**

A blood sample will be obtained for a next generation targeted deep sequencing genomic panel of 170 gene mutations prior to start treatment. Quantification of 5hmC and 5mC in patient's derived mononuclear cells will be obtained during the screening period and on C6D15 to evaluate for changes in methylation. We will use the ELISA, dot-blot and mass spec assay to measure the level of 5hmC, a signature for TET2 activity in HSPCs and 5mC an indicator of the lack of TET2 activity in patient derived PBMCs (Peripheral blood mononuclear cells) and bone marrow cells. For this purpose total genomic DNA from whole cell nuclear lysates (PBMCs or Bone marrow) or from the nuclear lysate of CD34+ cells will be extracted and used for ELISA assay using a known standard curve. The mass spec will be performed on the samples after digesting with NaOH (Ref: Nature 468, 839–843) and separated and quantified by LCMS-MS (Ref: Mo Cell; Volume 64, Issue 5, 1 December 2016, Pages 913–925) utilizing X-bridge reverse phase column. Recombinant TET2 protein will be used to prepare the standard reaction mixture for 5hmC determination and comparison to the patient samples.

All samples obtained will be shipped to and stored at The Cleveland Clinic. Samples will remain at the Cleveland Clinic to be used for research purposes for this study as well as for future research projects approved by the IRB.

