Secondary Objective(s)	
Secondary Endpoint(s)
 
 
1. The safety profile of the combination in the targeted patient population
 
2. Response duration
 
3. Overall survival of the treated population (compared to matched historical cohort of patients treated with single agent Azacitidine)
 
4. The identification of biomarkers that predict response to
 

	the combination
Correlative Objective(s)	Correlative Endpoint(s) Identify gnomonic biomarkers for response. Evaluate methylation profile and after treatment to determine its relation with response.
Sample Size	28
Disease sites/Conditions	Myelodysplastic Syndromes (MDS), MDS/MPN syndromes, and AML
Interventions	Azacitidine 75 mg/m  , SC / IV day (1-7) every 28 days cycle Ascorbic acid 1 g PO every day (daily) for every 28 days cycle

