### **2.2      Secondary Objective(s)**

To evaluate the following:

1. The safety profile of the combination of azacitidine and ascorbic acid in the targeted patient population.
2. The response duration for study patients.
3. The overall survival of the treated population (compared to matched historical cohort of patients treated with single agent Azacitidine)
4. The identification of genomic biomarkers that may predict response to the combination treatment.

5. Evaluation of changes in methylation prior and during therapy

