#### **4.1 Subject Selection**

#### **4.2 Inclusion Criteria**

Subjects must meet all of the following inclusion criteria to be eligible for enrollment:

4.2.1 Patients must have a confirmed *TET2* mutations identified by next generation targeted deep sequencing.

4.2.2 Patients must have MDS, or MDS/MPN overlap defined by 2016 WHO criteria. Both newly diagnosed or previously treated MDS or MDS/MPN patients are eligible as long as the patient has never received prior treatment with azacitidine or decitabine.

4.2.3 Patients with Leukemic/blast phase transformation MPN.

4.2.4 Patient with AML according to 2016 WHO criteria (excluding APL [AML-M3]).

4.2.4.1 Newly diagnosed patients who are ineligible or declined to receive intensive chemotherapy after discussion of risks and benefits of that approach or patients with primary refractory/relapsed AML.

4.2.4.2 Patients with active central nervous system (CNS) leukemia eligible at the discretion of treating physician.

4.2.4.3 Relapse/Refractory is defined as at least 1 course of treatment for AML excluding any patients treated with azacitidine or decitabine.

4.2.4.3.1 Patients should be off any prior treatment or line of therapy for 2 weeks prior to start study with the exception of hydrea (Hydroxyurea).

4.2.5 Prior therapy with hydroxyurea, biological or targeted therapy (e.g. flt3 inhibitors, other kinase inhibitors) or hematopoietic growth factors is allowed.

4.2.6 Age  $\geq 18$  years.

4.2.7 ECOG performance status  $\leq 3$ .

4.2.8 Patients must have normal organ and marrow function as defined at the discretion of the treating physician and PI.

- 4.2.9 Women of childbearing potential must have a negative serum or urine pregnancy test within 10-14 days prior to enrollment.
- 4.2.10 Patients must have the ability to understand and the willingness to sign a written informed consent document.
- 4.2.11 Patient must be willing to comply with all aspects of the protocol including completing the drug diary.
- 4.2.12 Patient must discontinue any and all use of multivitamin and/or vitamin c medication 24 hours before first dose of Ascorbic Acid.

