#### **Treatment Period (Day -3 to C6D28)**

1. Hematology exams (Appendix VI) at the start of each cycle (day 1) and the last day of cycle 6 (C6D28)
2. Serum Chemistry (Appendix VI), including Creatinine, bilirubin, ALT or AST at the start of each cycle (day 1)
3. Bone marrow aspirate and/or biopsy to confirm response, to be performed at the end of cycle 6. 10 ML of whole blood or bone marrow aspirate whichever available will be collected in extra lab tube. All bone marrows samples are to be stored at Cleveland Clinic
4. Conventional cytogenetics to be performed at the end of cycle 6
5. Documentation of frequency of transfusions (only PRBC and Platelets) prior to start of each new cycle.
6. Documentation in the medical record of any grade 2 or higher adverse events at each visit. For guidelines on SAE Reporting and AE entry for Case Report
7. Documentation of any prior administration of growth factors and ESA prior to start of each cycle
8. A 10 ML blood sample that will be used for next generation targeted deep sequencing of genes that are common in myeloid malignancies

9. Physical exam and ECOG performance status occurring at the end of each cycle
10. Vital signs occulting at each visit
11. Pregnancy test if applicable
12. MDS Response Assessment, assessed by the treating physician occurring at the end of cycle 6 or EOT, whichever occurs first.
13. Methylation panel only occurring in Cycle 1
14. Azacitidine will be administered intravenously or subcutaneously at a fixed dose of 75mg/m^2/day for 7 consecutive days, (allowing interruptions for weekends, and holidays, of each 28-day cycle).
15. Ascorbic acid will be administered orally daily at 1 g/day three days prior to start azacitidine and then continues daily for a total of 28 days of each 28 days cycle.

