## 11.2 Calendar

Period	Screening Period (Day-17 to Day -3)	Treatment Period														Extended Treatment Period Cycles	End Of Treatment (EOT)	Follow up k
		Cycle 1				Cycle 2		Cycle 3		Cycle 4		Cycle 5		Cycle 6				
Day		-3	1	7 c	14 n	1	7 c	28 g	1	7 c								
Administration of Azacitidine			X	X b		X	X b		X	X b								
Ascorbic Acid Dispensement		X a				X		X		X		X			X			
disease history and prior therapies	X																	
Record RBC/ platelets transfusion	X	X				X		X		X		X		X	X	X		
History and physical exam dm	X	X				X		X		X		X		X	X			X j
Vital signs d	X	X	X	X		X	X	X	X	X	X	X	X	X	X	X		X j
ECOG performance status em	X	X				X		X		X		X		X	X			X
Hematology dm	X	X				X	X	X	X	X	X	X	X	X	X	X		X j
Serum Chemistry d m	X	X				X		X		X		X		X	X			X
Pregnancy test	X														X			
Disease response assessment f	X														X	X		X
Bone marrow biopsy and aspiration L	X														X h			X i
Mutational analysis blood draw L	X l														X			
Methylation profile blood draw L	X		X	X	X													
Drug Diary Accountability		X				X		X		X		X		X	X	X		
Survival Follow up																		X k
Record adverse events m			↔ X →															

- A: For Cycle 1 only, patient will begin treatment with Ascorbic Acid 3 days prior to initial treatment of Azacitidine
- B: Azacitidine administration has a +/- 3 day window to account for breaks in treatment for weekends, and holidays
- C: Day 7 has a +/- 3 day window to account for breaks in treatment for weekends, holidays, and institutional standards
- D: See Appendix VI for required tests
- E: See Appendix I for performance status grading
- F: See Section for 12.0 for MDS/AML response assessment criteria
- G: If patient is eligible for the extended treatment period, and moving forward on the next cycle without a dosing delay, the C6D28 visit can serve as the visit of C7D1. If the patient is not eligible for the extended treatment period the patient's C6D28 visit can serve as the EOT visit.
- H: The cycle 6 bone marrow biopsy can occur up to 14 days (C6D14) prior to the C6D28 visit.
- I: EOT bone marrow biopsy is optional per discretion of the treating physician

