- J: These tests in follow up are optional pending discretion of the treating physician
- K: Survival Follow Up will occur bimonthly (60 days +/- 7 days) for a duration of 1 year from patient's EOT visit.
- L: 10 mL of whole blood or bone marrow aspirate whichever available will be collected in extra lab tube for these tests.
- M: If these procedures require a physician visit, these can occur 3 calendar days prior to the day 1 of that cycle (window of - 3 days).
- N: Cycle 1 Day 14 has a +/- 1 day window to account if the day falls on a holiday or weekend.

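### Section 10 plans methylation sampling at screening and C6D15, but Section 11 schedules no methylation draw after Cycle 1, so the late comparison has no scheduled sample

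*Combined protocol and SAP*

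**What the plan says.** Three places set the methylation schedule.

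- Section 10.0 (Exploratory or Correlative Studies): quantification of 5hmC and 5mC "will be obtained during the screening period and on C6D15 to evaluate for changes in methylation".
- Section 11.1, Treatment Period list, item 13: "Methylation panel only occurring in Cycle 1". No day is given.
- Section 11.2 calendar, row "Methylation profile blood draw": marks at screening, C1D1, C1D7 and C1D14, and none later.

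Two statements say what the samples are for. Section 2.2 lists as its fifth secondary objective "Evaluation of changes in methylation prior and during therapy". The protocol summary, under correlative objectives, says "Evaluate methylation profile and after treatment to determine its relation with response". Response is assessed after 6 cycles (Sections 12.0 and 14.0).

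Section 14.0 defines no methylation endpoint and no methylation analysis, so it does not settle which samples are to be compared.

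**The concern.** The schedules in Section 10 and Section 11 cannot both be followed as written. Section 10 bases its assessment of change on one on-treatment sample, in the middle of Cycle 6. Section 11 puts all on-treatment sampling in the first two weeks of Cycle 1. Nothing says which section governs.

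At stake is which samples exist when the change in methylation is analysed. The rationale for the combination is that ascorbic acid raises TET2 activity, and Section 10 treats 5hmC as the signature of that activity. A draw that was never scheduled cannot be made up later. Patients sampled under different readings of the protocol would also contribute different time points, in a trial of about 28 patients.

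**Working it through.** There is no stated figure to reproduce. The check sets the schedules side by side.

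| Source | Before treatment | On treatment |
|---|---|---|
| Section 10.0 | Screening | C6D15 |
| Section 11.1, Treatment Period, item 13 | Outside this list's scope | Cycle 1 only, day not given |
| Section 11.2 calendar | Screening | C1D1, C1D7, C1D14 |

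1. **Section 10 against the calendar.** The only shared time point is screening. No on-treatment time point is shared.
2. **Section 10 against Section 11.1 item 13.** No time point is shared, and the word restricting the panel to Cycle 1 excludes C6D15.
3. **Section 11.1 item 13 against the calendar.** These agree. Item 13 sits in a list that covers Day -3 to C6D28, so it does not contradict a screening draw. Section 10 is the outlier.
4. **Distance between the schedules.** With 28-day cycles and no delays, C6D15 is treatment day 5 × 28 + 15 = 155. The calendar's last methylation draw is treatment day 14. The gap is 155 − 14 = 141 days, or 141 / 28 ≈ 5.0 cycles. Visit windows of a few days cannot bridge it.
5. **Could the table extraction explain it?** The calendar header is broken in the text as read, but the row's marks clearly end at the fourth Cycle 1 column. Item 13 is plain prose and excludes Cycle 6 on its own.
6. **Does anything reconcile them?** No calendar footnote or amendment entry does so, and C6D15 appears nowhere else.
7. **Could Cycle 6 material exist anyway?** Section 11.1 (Treatment Period, item 3) collects an extra 10 mL tube with the end-of-cycle-6 marrow. Calendar footnote H lets that marrow be taken up to 14 days before C6D28, so from C6D14 to C6D28, which includes C6D15. Footnote L, attached to the marrow, mutational and methylation rows, says "10 mL of whole blood or bone marrow aspirate whichever available will be collected in extra lab tube for these tests". Nothing assigns the cycle 6 tube to methylation, and item 13 rules that use out.

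Scheduled samples under each reading:

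- Section 11 followed: screening against C1D1, C1D7 and C1D14 is available. No screening-to-C6D15 pair is scheduled.
- Section 10 followed: screening against C6D15 is available in patients still on treatment. No Cycle 1 samples are drawn.

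**The case against.** The strongest reply is that the operational sections agree and only Section 10 departs from them. The calendar gives a sample before therapy and three during it, which is what Section 2.2 asks for. C6D15 could also be a slip for C1D15: footnote N says "Cycle 1 Day 14 has a +/- 1 day window to account if the day falls on a holiday or weekend", and that window includes C1D15. On this reading the repair is a single correction in Section 10. Methylation is labelled correlative in the summary and has no planned test.

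Most of this stands. A reader might infer that no before-and-during comparison can be made at all; the calendar's screening and Cycle 1 draws show otherwise. The slip is plausible, but the documents do not confirm it, and the summary's aim of relating methylation after treatment to response gives an independent reason for a late sample. A correction is needed either way.

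Three further inferences are tempting but are not supported:

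- *That Section 10 forfeits a planned ascorbic-acid-alone contrast.* Ascorbic acid does start three days before azacitidine, so a C1D1 sample could bear on it, but no section plans that analysis.
- *That a Cycle 6 comparison would lose a known share of patients or be selected on outcome.* Treatment can end early through toxicity, withdrawal, clinical judgement or death, so the sample is limited to patients still treated. The documents give no dropout rate, and Section 6.4 counts lack of response as progression only after 6 months.
- *That vitamin C taken before baseline masks the change.* Inclusion criterion 4.2.12 requires stopping multivitamins and "vitamin c medication 24 hours before first dose of Ascorbic Acid", so a screening sample could be drawn while supplements are still in use. The documents do not quantify any effect, and stop dates are already recorded.

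**Conclusion.** The conflict is real and unresolved in the current text. Under Section 11, the screening-to-C6D15 comparison that Section 10 plans has no scheduled second sample; under Section 10, the Cycle 1 draws are not taken. The Section 2.2 objective can still be met from the calendar, so the loss is confined to the late time point and to the summary's aim of relating methylation after treatment to response.

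It would also go too far to say that Cycle 6 material is certain to be absent, because an unassigned tube is collected within a window that includes C6D15.

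The conclusion rests on the calendar row being read correctly, which item 13 supports, and on no document outside these naming a governing schedule. The primary response endpoint and the two-stage design are unaffected. The point deserves correction because it decides which samples are drawn for a listed secondary objective.

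**What to change.** Put one methylation schedule in Section 10.0, Section 11.1 and the Section 11.2 calendar, and name the paired time points for the change analysis.

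1. Keep the calendar's draws at screening, C1D1, C1D7 and C1D14, and state them in Section 10.0.
2. Decide whether a Cycle 6 comparison is intended.
   - If yes, add it to item 13 and to the calendar row by assigning to methylation the extra 10 mL tube already taken with the cycle 6 marrow (C6D14 to C6D28). Use the same tissue as the baseline sample, since footnote L allows either blood or marrow. Report the comparison as limited to patients still on treatment.
   - If no, correct C6D15 in Section 10.0.
3. Optionally, draw the baseline at the existing Day -3 visit before the first ascorbic acid dose, and report the supplement stop dates already collected under Section 11.1. The calendar's screening column already extends to Day -3. A blood baseline would then call for blood in the cycle 6 tube.

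The cost is wording in three places. No new visit or procedure is needed; if the Cycle 6 option is chosen, there is the added assay of a tube already being collected.
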